### **9.1.2. Relationship of Adverse Events to Study Treatment**

A summary of TEAEs by relationship to study treatment will be presented in a table. The investigator will provide an assessment of the relationship of the event to the study treatment. The possible relationships are "Not Related" and "Related". In the TEAE relationship table, if subject reports multiple occurrences of the same TEAE, only the most closely related occurrence will be

presented. Treatment-emergent AEs that are missing a relationship will be presented in the summary table as “Related” but will be presented in the data listing with a missing relationship. Percentages will be calculated based on the number of subjects in the safety set.

The TEAE data will be categorized and presented by SOC, PT, and relationship in a manner similar to that described in Section 9.1.1.

Additionally, the TEAE data will be categorized and presented by SOC, PT, relationship, and duration (1 day, 2 days,  $\geq 3$  days). The duration is calculated as the TEAE end date minus the TEAE start date, then add 1 day. At each combination level of relationship and duration, a subject is counted once if the subject reported one or more events. Percentages will be calculated out of the number of subjects in the safety set.

Treatment-emergent SAEs by relationship to study treatment will also be presented in a table. Treatment-emergent SAEs that are missing a relationship will be presented in the table as “Related” but will be presented in the data listing with a missing relationship.

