At Day 10, the TOC visit, the ibrexafungerp 600 mg dose showed clinical and mycological response rates in line with the reference fluconazole arm. Specifically, clinical cure was reported in 14 of 27 (52%) patients in the ibrexafungerp 600 mg dose arm and in 14 of 24 (58%) patients in the fluconazole arm. The percentage of patients showing a signs and symptoms score of 0 or 1 was also comparable, with 70% and 71% patients reporting this improvement in the ibrexafungerp 600 mg dose and fluconazole arms, respectively. The mycological eradication at this time point was 63% for both groups.

At Day 25, the follow-up (FU) visit, the ibrexafungerp 600 mg dose showed a trend towards improved clinical and mycological outcomes when compared to the fluconazole arm. If patients continued to have signs and symptoms of VVC at the TOC visit or later, rescue antifungal medication could be prescribed. Seven patients treated with fluconazole received rescue antifungal medication, whereas one patient treated with ibrexafungerp 600 mg received rescue antifungal medication. The rate of patients with no signs and symptoms (score = 0) at the FU visit was 70% for the ibrexafungerp 600 mg dose versus 50% for the fluconazole arm. A similar difference was observed when performing the analysis using a signs and symptoms score of 0 or 1, where this improvement was achieved by 81% of the subjects receiving ibrexafungerp 600 mg

dose versus 58% of the subjects receiving fluconazole. This demonstrates sustained symptom relief for at least 25 days and supports the monthly dosing proposed in this study

The oral ibrexafungerp 600 mg dose was generally well tolerated, with self-limiting (generally one-day duration), mild to moderate gastrointestinal AEs being the most commonly reported. Nausea was reported in three (10%) subjects in the ibrexafungerp 600 mg dose arm compared to two (6%) subjects in the fluconazole arm. Diarrhea and loose stool were reported in five (17%) subjects in the ibrexafungerp 600 mg dose arm compared to one (3%) subject in the fluconazole arm. Abdominal pain was reported in one (3%) subject in the ibrexafungerp 600 mg dose arm compared to 5 (16%) subjects in the fluconazole arm. No vomiting, severe AEs or discontinuations due to AEs were reported in the ibrexafungerp 600 mg dose arm.

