14.11 Dispensing, Completion, Review and Collection of Subject Diaries

All subjects will receive subject diaries that they will complete once a week from Day -14 to Day -1 of the Acute Phase and from Day 1 (Baseline) through Week 36 (EOFU) of the Prevention of Recurrence Phase of the study.

Diaries will be dispensed to all subjects on Day -14. At the Baseline (Day 1) visit of the study:

- Subjects who do not meet criteria to enter the Prevention of Recurrence phase of the study or to enter the Nested Sub-Study will be discontinued from the study and will have their diaries collected at that visit.
- Subjects who do not meet all criteria to enter the Prevention of Recurrence phase of the study but meet eligibility for the Nested Sub-Study will have their diaries collected for review and redispensed at the Sub-Study Baseline visit (see Sub-Study details in [Section 21.3](#) [Appendix C]).
- Subjects who are eligible to enter the Prevention of Recurrence Phase of the study will have their diaries collected and dispensed every three 4-week period, i.e., at Baseline (Day 1), Week 12, Week 24 (TOC), Week 36 (EOFU, diary collection only).

Subject diaries will be reviewed at all on-site visits (Baseline [Day 1], Week 4, Week 8, Week 12, Week 24 [TOC], Week 36 [EOFU]) and unscheduled visits.

The subject diaries will include the Vulvovaginal Signs and Symptoms (VSS) Scale so that subjects can rate their vulvovaginal symptoms (see [Section 14.9](#) for symptom rating procedures and [Section 21.2](#) [Appendix B] for the full VSS Scale). Subjects will record the date of study medication dosing, vulvovaginal symptoms rated on a weekly basis and at the time of each scheduled or unscheduled visit to the site, other medical concerns or complaints and concomitant medications used.

The site will determine if any signs/symptoms or other medical concerns/complaints recorded on the diary should be reported as AEs. The information from the subject diary will be reviewed by the site and relevant findings will be included in the corresponding eCRFs modules (e.g. concomitant medications, AEs, etc.).

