### 9.1. Adverse Events

An AE is any untoward medical occurrence associated with the use of a drug in humans, whether or not considered drug related. An AE can therefore be any unfavorable and unintended sign (including an abnormal laboratory finding), symptom or disease temporally associated with the use of a study drug/study intervention, whether or not related to the study drug/study intervention.

A prior adverse event (PAE) is defined as adverse event whose start date is before the date of the first dose of study treatment. For subjects who didn't take study treatment, all AEs will be identified as PAE. A Summary of the total number of PAE and the number and percentage of subjects with at least one PAE will be provided by SOC and PT based on all screened patients. Besides, a subject listing will be presented for all the prior adverse events.

A TEAE is defined as any event does not present before exposure to study drug or any event already present that worsens in either intensity or frequency after exposure to study drug.

For the purpose of inclusion in TEAE tables, incomplete AE start and end dates will be imputed as follows:

Incomplete onset dates (where UK and UNK indicate unknown or missing day and month respectively):

- UK-*MMM*-*YYYY*: If the month and year are different from the month and year of the date of first dose, assume 01-*MMM*-*YYYY*. If the month and year are the same as the month and year for the date of first dose, and the end date (after any imputation) is on or after the date of first dose, then assume the date of first dose. If the month and year are the same as the date of first dose, and the end date (after any imputation) is prior to the date of first dose, then assume the end date for the start date.
- *DD*-UNK-*YYYY*/UK-UNK-*YYYY*: If the year is different from the year of the date of first dose, assume 01-JAN-*YYYY* of the collected year. If the year is the same as the date of first dose year, and the end date (after any imputation) is on or after the date of first dose, then assume the date of first dose. If the year is the same as the date of first dose, and the end date (after any imputation) is prior to the date of first dose, then assume the end date for the start date.

Incomplete end dates (where UK and UNK indicate unknown or missing day and month respectively):

- UK-MMM-YYYY: Assume the last day of the month;
- DD-UNK-YYYY/UK-UNK-YYYY: Assume 31-DEC-YYYY.

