The missing onset dates will be imputed as the date of first dose of study drug. The missing end date will be imputed as the subject's last visit date.

All adverse events will be classified by SOC and PT according to the Medical Dictionary for Regulatory Activities (MedDRA, Version 19.1 or higher).

An overview summary of the number and percentage of subjects with any TEAE, serious TEAE, treatment-related TEAE, treatment-related serious TEAE, TEAE leading to study treatment discontinuation, TEAE leading to study discontinuation, and AE leading to death will be provided by treatment group and study period (prior or on TOC visit, after TOC visit but prior or on EOFU visit, and entire study).

All AEs will be presented in a listing.

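### SAP 9.1.2 does not exclude imputed end dates from TEAE duration; if they are used, about 93% of one-day events with an unknown stop day appear as 3 days or more

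*SAP*

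**What the plan says.** SAP 9.1.2 orders a table in which "the TEAE data will be categorized and presented by SOC, PT, relationship, and duration (1 day, 2 days", with 3 days or more as the top class. The formula is stated in one sentence: "The duration is calculated as the TEAE end date minus the TEAE start date, then add 1 day". A subject counts once at each combination of relationship and duration, and percentages are taken over the safety set. The section does not mention incomplete dates.

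Those are handled only in SAP 9.1, under the lead-in "For the purpose of inclusion in TEAE tables, incomplete AE start and end dates will be imputed as follows". The end-date rules are:

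- day unknown: "UK-MMM-YYYY: Assume the last day of the month"
- month unknown: "DD-UNK-YYYY/UK-UNK-YYYY: Assume 31-DEC-YYYY"
- no date at all: "The missing end date will be imputed as the subject's last visit date"

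Protocol 7.1 describes the Phase 2b experience at the 600 mg dose as "self-limiting (generally one-day duration), mild to moderate gastrointestinal AEs being the most commonly reported".

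**The concern.** The SAP 9.1 rules place the end date as late as possible. That is a sensible convention for deciding whether an event counts as treatment-emergent, but it does not estimate how long the event lasted. Fed into a subtraction with cut-points at 1, 2 and 3 days, it sends nearly every short event with an incomplete stop date to the longest class.

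The cut-points match the property that the protocol claims for the drug's common gastrointestinal events, namely that they generally last one day. An error here falls on the boundary that the table exists to show. Incomplete stop dates can arise, because the diary is kept weekly: "All subjects will receive subject diaries that they will complete once a week". What is at stake is the reading of one safety table.

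**Working it through.** The plan gives no figure of its own on this point, so there is none to reproduce. The check first asks which dates the table uses, then what follows if they are the imputed ones.

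**1. Which dates?** Four things point to imputed dates:
- The duration table is a TEAE table, and the SAP 9.1 rules are given for TEAE tables.
- No other rule covers incomplete adverse event dates.
- SAP 9.1.3 requires a Missing row for severity; SAP 9.1.2 names none for duration.
- SAP 7.1 leaves a wholly unknown medication stop date missing and treats the medication as ongoing, whereas SAP 9.1 fills in the last visit for an adverse event.

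Two things point the other way. The stated purpose of the rules is inclusion in the tables, and the only explicit use of an imputed end date is to resolve a partial onset date. The sub-study plan repeats the imputation text (SAP 13.4.9.1) but has no duration table (SAP 13.4.9.1.2). This fits rules written for treatment-emergence, with duration added to the main study without a rule of its own. Imputed dates are therefore the natural reading, but not a stated one.

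**2. Stop month known, day unknown.** Take a true one-day event with a complete start date, every calendar date being equally likely (an assumption). In a month of L days, with start on day d, the imputed duration is L − d + 1.
- Example: start on the 3rd gives 30 − 3 + 1 = 28 days, or 31 − 3 + 1 = 29 days.
- The result is below 3 only on the last two days of a month. In a leap year that is 12 × 2 = 24 dates, leaving (366 − 24)/366 = 342/366 = 93.4% at 3 days or more.
- Over all dates from 2019 to 2022: 93.4% at 3 days or more, 3.3% at 2 days, 3.3% at 1 day; mean imputed duration 15.7 days.
- For a true two-day event, 96.7% are shown as 3 days or more.

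**3. Only the year known.** The end becomes 31 December, so only starts on the last two days of the year escape. Over 2019 to 2022 that leaves 99.5% at 3 days or more, with a mean of 183 days.

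**4. Stop date missing.** The end becomes the last visit. Dosing is on Day 1 and at Weeks 4 to 20 (Days 28, 56, 84, 112 and 140). Week 24 is Day 168, and Week 36 is 36 × 7 = Day 252.
- Last visit Day 168: from 168 − 140 + 1 = 29 to 168 − 1 + 1 = 168 days.
- Last visit Day 252: from 252 − 140 + 1 = 113 to 252 − 1 + 1 = 252 days.
- With uniform onset, 1 − 2/168 = 98.8% and 1 − 2/252 = 99.2% are shown as 3 days or more. An event that starts on the day of the last visit would stay at 1 day.

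**5. With imputed dates excluded from duration,** the share of these one-day events placed in the longest class by imputation falls to 0%. They move to a row that says their duration is not known.

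**The case against.** The case against is substantial.

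- **Date quality is provided for.** Protocol 16.10 asks that the duration of each adverse event be determined, and Protocol 16.12 requires follow-up to resolution or another outcome. Protocol 14.22 and 10.1.1.3.1 have adverse events assessed at every visit, phone contacts included. Incomplete stop dates may be rare. This stands, and it is why no size can be given for the effect on the table.
- **A Missing row may already exist.** SAP 4 allows one wherever the table shells specify it, and the shells are not among the documents. This stands for the row. It does not settle which dates feed the calculation.
- **Events truly ongoing at the last visit** will usually have lasted at least 3 days, so the top class is right for them. This stands, and the fix keeps them there.
- **Using only complete dates would introduce its own bias.** An event that starts on 3 March and stops on an unknown day in April cannot have ended before 1 April, so it lasted at least 30 days. Dropping such events would make harm look shorter. This stands, and it shapes the fix.
- **Any error lengthens apparent duration,** which is cautious for safety. True, but a table meant to separate one-day events from longer ones should not depend on a date convention.

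**Conclusion.** The SAP leaves open whether imputed end dates set the duration class, and its wording leads most naturally to their use. If they are used, a true one-day event is shown as 3 days or more for about 93% of start dates when the stop day is unknown, and for about 99% when only the year is known or the stop date is missing. These shares assume onset spread evenly over the dates considered. They apply only to events with incomplete stop dates, and the documents give no rate for those.

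A reader might infer more, but the documents do not support it:
- That the SAP states that imputed dates are used: SAP 9.1.2 refers only to the TEAE start and end dates.
- That the shift in the published percentages can be quantified: this needs the rate of incomplete stop dates and the true share of long events, and the documents give neither. The table also counts subjects over the safety set, not events.
- That the comparison between arms is distorted: the same rule applies to both arms, no safety test is planned, and no rate of incomplete dates by arm is given.
- That events after the Week 16 dose are first examined at Week 24: diary review is tied to on-site visits, but the Week 20 call also asks about adverse events.

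The effect is confined to one descriptive safety table; no efficacy or inferential result depends on it. Severity is minor.

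**What to change.** Add to SAP 9.1.2:

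1. Dates imputed under SAP 9.1 serve only to decide treatment-emergence and are not used for duration.
2. Duration is computed from observed start and end dates.
3. An event stays in the class of 3 days or more when its known date parts prove it, or when it is still ongoing at a last contact at least 3 days after onset.
4. All remaining events go in a row labelled *duration not determinable*.

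The cost is a few lines of text and one table row, with no new data. The small downside is that some events will have no duration class.

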### **9.1.3. Severity of Adverse Event**

A summary of TEAEs by severity will be presented in a table. The severity that will be presented represents the most extreme severity captured on the CRF page. The possible severities are “Mild”, “Moderate”, and “Severe”.

In the TEAE severity table, if a subject reported multiple occurrences of the same TEAE, only the most severe will be presented. An additional row “Missing” must be added for the missing severity. Percentages will be calculated out of the number of subjects in the safety set.

The TEAE data will be categorized and presented by SOC, PT, and severity in a manner similar to that described in Section 9.1.1.

Additionally, the TEAE data will be categorized and presented by SOC, PT, severity, and relationship. At each combination level of severity and relationship, a subject is counted once if the subject reported one or more events. Percentages will be calculated out of the number of subjects in the safety set.

Treatment-emergent SAEs by severity will also be presented in a table.

### **9.1.4. Adverse Events Leading to Treatment Discontinuation**

A summary of the TEAEs with an action taken with study treatment of “Drug Withdrawn” will be presented by treatment in a manner similar to that described in Section 9.1.1.

Any TEAEs leading to treatment discontinuation will be presented in a listing for all subjects.

### **9.1.5. Adverse Events Leading to Study Discontinuation**

All subjects who have an AE with the answer to “Caused Study Discontinuation” is “Yes” will be presented in a listing.

### **9.1.6. Death**

All subjects who have an AE with an outcome of “Death Related to Adverse Event” will be presented in a listing.

## **9.2. Clinical Laboratory Evaluations**

Summary tables will be presented for laboratory test results (hematology and blood chemistry) by treatment at Screening and the scheduled post-treatment visits for subjects in the safety set.

All relevant clinical laboratory tests in chemistry and hematology will be classified as Low, Normal, and High according to the normal ranges. This categorical data will be summarized in shift tables comparing the extreme results at post-treatment study scheduled visits with those at the baseline visit. Extreme post-baseline results will also be summarized. When there are multiple values within a visit for a particular laboratory variable, the worst value will be taken (worst being the smallest value for criteria below a certain threshold or the largest value for criteria above a certain threshold). If a subject has a value below the threshold and above the threshold, the value furthest from the threshold will be chosen.

Plots of average clinical laboratory parameters may be presented.

In data listings, laboratory values will be compared to normal ranges; out-of-range values will be identified.

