14.12 Sample Collection for Safety Laboratory Tests

Safety laboratory tests will be performed by a qualified central laboratory. Blood samples for safety laboratory tests will be collected at the Days -4 to -2 visit (Acute Phase, lab visit only) to determine subject eligibility. Lab results will be reviewed at Baseline (Day 1). Additional samples will be collected at Week 12 and at unscheduled visits, if needed. If indicated, these may be done at Week 36 to follow up on a laboratory abnormality.

The following laboratory parameters will be determined:

Hematology

- White blood cell (WBC) count
- Red blood cell (RBC) count
- Platelet count
- Differential WBC count will include percentages for lymphocytes, monocytes, eosinophils and basophils, and absolute counts for neutrophils, lymphocytes, atypical lymphocytes, monocytes, eosinophils and basophils.
- Hemoglobin
- Hematocrit

Blood Chemistry

- Glucose
- Hemoglobin A1C (glycosylated hemoglobin)
- Albumin
- Sodium
- Potassium
- Alkaline Phosphatase
- Creatinine
- Blood Urea Nitrogen (BUN)
- Total creatine phosphokinase (CPK)
- Aspartate aminotransferase (AST/SGOT)
- Alanine aminotransferase (ALT/SGPT)
- Gamma glutamyl transferase (GGT)
- Bilirubin (total, direct and indirect)
- Total protein

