18.7.2 Analyses

No formal statistical analysis is planned for the safety data. Safety analyses will be conducted using the safety population. AEs will be coded using the Medical Dictionary for Regulatory Activities (MedDRA) Version 19.1 or higher. The incidence and severity of treatment-emergent AEs and SAEs and their relationship to treatment will be summarized by system organ class and preferred term. The percentage of subjects who discontinued study treatment and the reasons for discontinuation will be summarized by treatment group.

Laboratory evaluations and vital signs will be summarized as observed values and as changes from Baseline by treatment group. In addition, shifts (with respect to the reference range) from Baseline will be presented for laboratory tests by treatment group.

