#### **11. Changes in the Planned Analysis**

The following have changed from the protocol:

- For the continuous efficacy endpoints except for the absolute number of Mycologically Proven, Presumed or Suspected Recurrences from Baseline (Day 1) to Week 24 (TOC) and Week 36 (EOFU), a Mixed-Effect Model for Repeated Measure (MMRM) analysis model and an analysis of covariance (ANCOVA) model are recommended rather than a two-way ANOVA model. Baseline value will be considered as possible contributor to any observed differences. Additionally, other variables may be considered during blinded data review.
- Add the randomization stratification factor, uncontrolled diabetes mellitus (Yes or No), as justification factor in the efficacy analyses models.

- For efficacy analyses, Country is recommended rather than site to be used as the justification factor.
- In protocol, it stated that the safety and tolerability as measured by AEs, vital signs, treatment discontinuation and safety laboratory tests at TOC (Week 24). The texts “at TOC (Week 24)” is removed since all safety data captured in this study will be taken into account for analysis.
- Intent-to-treat (ITT) Set definition was changed to be “All randomized subjects who signed the consent form and received at least one dose of study drug (ibrexafungerp or placebo).”
- Modified Intent-to-treat (mITT) Set definition was changed to be “All randomized subjects who signed the consent form and received at least one dose of study drug (ibrexafungerp or placebo), who have a confirmed mycological culture for yeast at Screening and a negative culture for yeast at Baseline (Day 1).”
- The number of recurrence episodes will be classified to 4 order categories for analysis rather than 3 categories as mentioned in the protocol. Updated based on client’s request.

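### The SAP's laboratory shift tables use scheduled visits only, so a transient abnormality found at an unscheduled draw has no stated route into them; the protocol's laboratory change-from-baseline summary is also missing

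*SAP*

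**What the plan says.** SAP 9.2 classifies each hematology and chemistry result as low, normal or high and then states: "This categorical data will be summarized in shift tables comparing the extreme results at post-treatment study scheduled visits with those at the baseline visit". Its other laboratory summaries are also set at scheduled post-treatment visits. It adds that "Extreme post-baseline results will also be summarized", without saying which draws count or how that output is laid out. Two selection rules follow. One covers repeats: "When there are multiple values within a visit for a particular laboratory variable, the worst value will be taken". The other covers a woman with results on both sides of the range: "If a subject has a value below the threshold and above the threshold, the value furthest from the threshold will be chosen".

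Protocol 14.12 fixes the draws. There is one before randomization (Days -4 to -2), and then: "Additional samples will be collected at Week 12 and at unscheduled visits, if needed". For the last visit: "If indicated, these may be done at Week 36 to follow up on a laboratory abnormality". The schedule in SAP Appendix 1 agrees and shows no laboratory draw at Week 24.

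Protocol 18.7.2 plans shifts from Baseline by treatment group with no restriction to scheduled visits. It also says: "Laboratory evaluations and vital signs will be summarized as observed values and as changes from Baseline by treatment group". SAP 9.3 carries the change from baseline over for vital signs. SAP 9.2 does not do so for laboratory tests. The list of changes in SAP Section 11 mentions neither point.

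**The concern.** A shift table to the extreme value is meant to show, by arm, how many women moved from normal to abnormal at any time on treatment. Here the extreme is taken over a set of visits that usually holds one result. Unscheduled draws, which are taken when there is a reason to look, are outside that set as worded, and the SAP has no rule for assigning them to a scheduled visit.

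The table could therefore show few or no shifts in an arm where transient abnormalities were found. A reader who takes the word extreme at face value would not know that. Without the change from baseline, the by-arm view of laboratory movement is thinner than the protocol promised.

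**Working it through.** The plan states no figure on this point, so there is nothing to reproduce. The check is a count of draws, a comparison of the texts, and an illustration of scale.

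**Draws that can feed the shift table**

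- Routine draws after the first dose: 1 (Week 12, Day 84).
- Conditional draws at a scheduled visit: 1 (Week 36), only to follow up an abnormality.
- Week 24: none.
- Unscheduled visits: drawn if needed; not included in the shift-table wording.

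For a woman with no abnormality to follow up, the extreme over scheduled visits is one number, the Week 12 value. A woman who leaves before Week 12 has the Week 24 procedures at exit (Protocol 11.3), and these include no draw. Any unscheduled draw would be her only result after dosing, and the table has no stated place for it.

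**Routes for an abnormality first seen at an unscheduled draw**

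1. It is still present at Week 12, or persists to a Week 36 follow-up draw: it enters the shift table.
2. It is assigned to a scheduled visit and picked up by the worst-value-within-a-visit rule: possible in principle, but the SAP gives no assignment rule.
3. It resolves outside those draws: no stated route.

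**Where else the value can appear**

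- Extreme post-baseline summary (SAP 9.2): no scheduled-visit limit, but no stated cross-classification by baseline status.
- Liver summary (SAP 9.2.2): any post-baseline visit, but it uses ALT, AST and total bilirubin only. Protocol 14.12 lists 6 hematology and 14 chemistry entries, 6 + 14 = 20, some of which cover several measurements.
- Adverse event tables (Protocol 16.1, SAP 9.1.1): by arm, but only if the investigator judges the abnormality clinically significant.
- Listings: out-of-range values are flagged, but listings are not a comparison of arms.

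**Change from baseline**

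Protocol 18.7.2 requires it for laboratory tests and vital signs. SAP 9.3 plans it for vital signs. SAP 9.2 is silent, although SAP Section 4 defines the term in general.

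**Scale (assumed rates only)**

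With 240 / 2 = 120 women per arm, let u be the share with an unscheduled draw and a the share of those with a new out-of-range value. The number who could be missing from the shift table is at most 120 × u × a.

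- u = 5%, a = 20%: 120 × 0.05 × 0.20 = 1.2
- u = 20%, a = 50%: 120 × 0.20 × 0.50 = 12

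These are upper bounds for the chosen rates, because a woman who is also abnormal at Week 12 or Week 36 would be counted.

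**The case against.** The strongest reply is that the information is not lost. The extreme post-baseline summary has no scheduled-visit limit, the liver events are counted at any visit, clinically significant abnormalities become adverse events, and the listings flag the rest. The layout of the extreme summary is also unspecified, so it might show baseline status. This stands as far as it goes: the gap is in the shift table, not in the whole safety analysis. But the SAP does not commit any of these outputs to showing shift from baseline by arm for all tests.

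Four stronger readings are tempting, and the documents do not support them.

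- A reader might infer that unscheduled findings can never enter the shift table. They can, if they are present at Week 12 or persist to a Week 36 draw.
- A reader might infer that SAP Section 11 contradicts 9.2, because it says that "all safety data captured in this study will be taken into account for analysis". That sentence explains why the Week 24 limit was removed from the safety endpoint. It does not promise that every table uses every draw.
- A reader might blame SAP 9.2 for the lack of routine laboratory data late in treatment: the dosing days at Weeks 12, 16 and 20, 3 of 6, have no routine draw on a later day. That follows from the sampling schedule, and rewording 9.2 adds no draws.
- A reader might infer that the two-sided rule already hides serious low values behind small high ones. It needs two results on opposite sides, which is uncommon when there is usually one, and the SAP does not say how distance is measured. The rule would matter more once all draws are used.

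A fair point against the remedy is that unscheduled visits follow recurrence symptoms or adverse events. The design assumes success of 65% and 43%, so failure of 100 - 65 = 35% and 100 - 43 = 57%. The arms may therefore differ in how often unscheduled draws occur, and a worst-over-all-draws table would partly reflect that.

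**Conclusion.** The point holds in a limited form. The laboratory shift tables are worded more narrowly than Protocol 18.7.2, the narrowing is undeclared, and a transient abnormality found only at an unscheduled draw has no stated route into them. Separately, SAP 9.2 does not plan the laboratory change-from-baseline summary that the protocol requires. This is an omission by silence, since Section 11 does not say it was removed.

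The size cannot be fixed from the documents, which give no rate of unscheduled draws. The figure of roughly 1 to 12 women per arm rests entirely on the assumed rates above and is an upper bound for each pair of rates. Safety analysis here is descriptive, so no test is affected, and efficacy is untouched. The change is still worth making, because the by-arm laboratory picture is thinner than the protocol describes.

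**What to change.** In SAP 9.2:

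1. Define the shift as baseline category against the lowest, and separately against the highest, post-baseline value from any scheduled or unscheduled draw. With two panels the furthest-from-threshold rule is not needed and can be deleted.
2. Keep the scheduled Week 12 summary beside it, as the view with the same planned draw in both arms.
3. Add the laboratory change from baseline at Week 12, as Protocol 18.7.2 requires.
4. State that the extreme post-baseline summary uses the same set of draws.
5. Footnote the shift tables with the number of draws per arm, so that a difference in draw frequency is visible.

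The cost is SAP wording and table programming; no new samples are needed. The downsides are one more shift panel and abnormality counts that may partly reflect how often each arm was sampled, which items 2 and 5 let the reader judge.
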